### **6.2.7 Rationale for Control Condition**

The selection of our control group was influenced by several factors. There are currently only 20 Prisma Health primary care clinics that have not received EIMG onboarding and activation and that are within 15 miles or less of a participating community PA facility. There are no other equivalent Prisma Health primary care clinics to serve as matched controls (i.e., via a stepped wedge design). We are then left with two groups of clinics to serve as controls. The first of these is using a within-clinic design and comparing patient health outcomes before and after the dissemination of the initial EIMG Instructional Video. Secondly, from past experiences, we anticipate that several of the 20 clinics will choose not to adopt EIMG and/or will be non-responsive to our invitation. As one of our study aims, we will evaluate contextual factors and differences between adopting and non-adopting clinics. Clinics that do not adopt EIMG will not be 'activated' and can therefore serve as control clinics, particularly when evaluating patient-level outcomes, as none of their patients will have had the opportunity to participate in EIMG.

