### **8.3 Phase II – EIMG Instructional Video**

Phase II will start with disseminating the EIMG Instructional Video to adopting clinics, followed by EIMG activation. The EIMG Instructional Video is intended to be a low-intensity strategy for disseminating information and guidance on EIMG and the PA referral pathway connecting Prisma Health primary care clinics and the community PA facilities. The EIMG Instructional Video is a brief (11-minute), voice-over PowerPoint presentation that provides information on: a) the origins of EIMG, b) the 12-week, community-based PA program, c) initial patient effectiveness results, and d) process for placing an EIMG referral. The EIMG Instructional Video will be sent to the practice managers at EIMG-adopting clinics for broader dissemination to all

clinic staff. After delivery of the EIMG Instructional Video to the practice managers, access to the EIMG referral process in the EHR is *'turned on'* (aka – EIMG activation) allowing clinic staff to electronically identify and engage with eligible patients.

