$E_{ijk}$  equals 1 if patient “i” in the episode at clinic “j” in the “k-th” month after study initiation was referred to EIMG, 0 otherwise;  $X_{ijk}$  represents patient-specific baseline demographic, clinical, and socioeconomic factors,  $L_j$  are a series of binary variable for each Prisma clinic “j”,  $M_k$  is a count variable representing the number of months since the beginning the study that contains patient “i’s” index date, and  $C_{ijk}$  equals 1 if the episode occurred in a period in which the clinic “j” received or had previously received EIMG activation, 0 otherwise. The parameters  $\omega_j$ ,  $u_k$ , and  $\epsilon_{ijk}$  represent the model random effects associated with site “j”, month “k”, and patient “i”, respectively. We will estimate equation (1) using a generalized linear mixed model. The estimate of parameter  $\beta_4$  equals the effect of standardized EIMG training on the probability of the patient within the episode being referred to EIMG. Variables within  $X_{ijk}$  will include patient history of EIMG use. Our stepped wedge design will enable us to directly control for unmeasured factors associated with site and time. Secondary analyses will assess differences in the impact of standardized EIMG training by stratifying by eligible conditions (i.e., overweight/obese, hypertension, type 2 diabetes).

While EIMG activation will be randomly assigned to clinics using the stepped wedge design, actual EIMG referral decisions will remain at the discretion of provider and patient. As a result, referral decisions for some patients will be “non-compliant” at the clinical level. Providers may refer patients into EIMG based on factors unmeasured by the researcher that are related to study outcomes which can confound estimation of the effect of EIMG on study outcomes. With non-compliance, it is problematic to use “as treated” EIMG referral variation to assess the effects of EIMG referrals on study outcomes. Instrumental variable (IV) methods using randomized EIMG activation as an “instrument” will be used to avoid confounding problems. In this scenario IV estimation will yield consistent estimates of the effect of EIMG referral on study outcomes for the subset of patients whose referrals are responsive to the randomized clinical-level EIMG activation. This is known as the Complier Average Causal Effect (CACE). The CACE model is specified as:

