$$(3) \quad Y_{ijk} = \alpha_0 + \alpha_1 \cdot X_{ijk} + \alpha_2 \cdot L_j + \alpha_3 \cdot M_k + \alpha_4 \cdot \hat{E}_{ijk} + \rho_j + \tau_k + \vartheta_{ijk}, \text{ where}$$

$\hat{E}_i$  equals the *predicted probability* of that patient “i” is referred to EIMG from equation (2); and the other variables defined as in equation (2). The parameters  $\rho_j$ ,  $\tau_k$ , and  $\vartheta_{ijk}$  represent the random effects associated with site “j”, month “k”, and patient “i”, respectively. The estimated parameter  $\alpha_4$  on  $\hat{E}_{ijk}$  is the CACE or the average treatment effect for patient subset whose EIMG referral was influenced by EIMG activation at the clinic.  $C_{ijk}$  in equation (2) serves as the “instrument” and only the portion of variation in  $\hat{E}_{ijk}$  stemming from  $C_{ijk}$  is used to estimate  $\alpha_4$ . Because  $C_{ijk}$  will be randomly assigned, EIMG referral variation stemming from this assignment will be independent of unmeasured confounding variables. Two-stage least squares (2SLS) IV estimators will be used to estimate the effects of EIMG referrals induced by clinical-level EIMG activation on study outcomes. For each study outcome, equation (2) will serve as the first stage

equation of 2SLS, and second stage model will be equation (3). Because our expected sample sizes will be greater than 500 *our 2SLS estimates will be distributed normally via the central limit theorem regardless of the distribution of the underlying error term.* Each 2SLS model will be estimated with robust standard error methods appropriate for 2SLS models using STATA to account for error structure in equation (3).

Define  $\alpha_{4C}$  as the 2SLS estimate when episode healthcare cost is the dependent variable in equation (3) and  $\alpha_{4H}$  as the 2SLS estimate when a health outcome change is the dependent variable in equation (3). Combining these estimates with the estimates of average patient EIMG training costs from Section F3.2 yields the following cost-effectiveness ratio of EIMG relative to standard care:

$$(4) \text{ EIMG Cost Effectiveness Ratio} = \left[ \frac{(\text{EIMG Training Costs per Patient} + \alpha_{4C})}{\alpha_{4H}} \right]$$

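### Section 12.5.5 names two incompatible first stages for the Aim 2 instrumental-variable analysis: a generalized linear mixed model feeding predicted probabilities into equation (3), and 2SLS

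*Combined protocol and SAP*

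**What the plan says.** Section 12.5.5 defines E as 1 if the patient in an episode was referred and 0 otherwise. Equation (2) models E on patient covariates X, clinic indicators L, a month count M and the instrument C, with further random terms for site and month. C is coded as 1 once the clinic has been activated.

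On estimation, the section says "We will estimate equation (1) using a generalized linear mixed model". Equation (1), in Section 12.5.4, is the training-cost ratio. No link function is given. E-hat in equation (3) is then defined as the predicted probability of referral from equation (2).

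The section continues: "Two-stage least squares (2SLS) IV estimators will be used to estimate the effects of EIMG referrals induced by clinical-level EIMG activation on study outcomes". It makes equation (2) the first stage and equation (3) the second, claims that E-hat contributes to alpha_4 only through C, and adds "Each 2SLS model will be estimated with robust standard error methods appropriate for 2SLS models using STATA".

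Two other sections bear on the data. In Section 8.3, once the video has been delivered, "access to the EIMG referral process in the EHR is" switched on. In Section 6.2.7, non-adopting clinics can act as controls because "none of their patients will have had the opportunity to participate in EIMG".

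**The concern.** The stated property, that only C drives the estimate, belongs to a linear projection. If E-hat comes from a non-linear model it carries extra variation in X and month through the link, and equation (3) will use that variation. The estimate then rests partly on functional form, which is what the instrument was meant to avoid.

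An analyst who follows the mixed-model sentence and one who follows the 2SLS sentence would report different values of alpha_4. Both alpha_4C and alpha_4H enter the cost-effectiveness ratio in equation (4), which is repeated by diagnosis. Section 12.5.5 gives no rule for choosing between the two, so the choice could be made after the data are seen.

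A second difficulty follows from the design. If nobody can be referred without activation, a logit or probit first stage is separated on C.

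**Working it through.** The plan gives no power or first-stage strength for Aim 2, only an expectation of more than 500 observations, so there is no figure to reproduce. The check is algebra, then simulation.

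**1. Which variation identifies alpha_4.** Let W stand for X, the clinic indicators and month, all of which are also in equation (3).
- Linear first stage: E-hat = W·pi + beta_4·C. After W is partialled out, what remains is beta_4 times the residual of C, so 100% comes from C.
- Logit first stage: E-hat = 1/(1 + exp(-(W·pi + beta_4·C))). After W is partialled out, C-by-X and C-by-month products and curvature also remain. If the outcome depends on X in a way that equation (3) omits, E-hat stands in for it.

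**2. Separation.** Suppose E = 0 whenever C = 0. Hold beta_0 + beta_4 fixed and let beta_4 grow. The fit at C = 1 does not change, while each log(1 - p) at C = 0 rises towards 0. The likelihood therefore has no maximum at a finite beta_4. Both outcomes occur at C = 1, so this is quasi-complete separation. The indicator of any clinic with no referrals diverges in the same way, however C is coded. With an identity link beta_4 is finite.

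**3. Simulation inputs.**
- From Section 12.3: referral rising from 0.001 to 0.01 over four months, then a step of 0.02 (0.01 + 0.02 = 0.03), reaching 0.04 at month 8.
- From Sections 6.2.7 and 8.3: referral 0 without activation.
- Assumed: 12 adopting and 8 non-adopting clinics; 4 months before and 8 after activation; one measured covariate X; one unmeasured confounder; outcome residual SD 1; true alpha_4 = -2.
- The logit used X, month and C only, without clinic indicators or random effects. The linear first stage and both second stages had clinic indicators.

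**4. One data set, 150 episodes per clinic-month.** N = 20 × 12 × 150 = 36,000, of which 12 × 8 × 150 = 14,400 have C = 1. There were 271 referrals at C = 1 (271/14,400 = 1.9%) and none at C = 0.

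| Newton iteration | logit beta_4 | log-likelihood |
|---|---|---|
| 6 | 5.9 | -1241.278 |
| 12 | 11.9 | -1240.699 |
| 18 | 17.9 | -1240.698 |
| 24 | 23.9 | -1240.698 |

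The coefficient rises by about 1 per iteration while the likelihood is flat. The linear first stage gave beta_4 = 0.00885 with clinic-clustered SE 0.00308, so F = (0.00885/0.00308)² ≈ 8.3. In separate data sets with a few referrals at C = 0, the logit estimate was finite: 3.4 with 7 such referrals and 2.3 with 22.

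**5. Second stage, 150 runs, 100 episodes per clinic-month, true value -2.** The logit plug-in used the limiting fitted probabilities, which are 0 at C = 0.

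| Covariate form | Linear 2SLS, mean (SD) | Logit plug-in, mean (SD) | Share of residual E-hat variation from C, logit |
|---|---|---|---|
| Correct | -2.6 (3.1) | -1.8 (0.7) | 4.5% |
| X² omitted (0.4 in referral, 0.5 in outcome) | -2.2 (1.9) | +4.0 (0.6) | 3.0% |

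The Monte Carlo standard error of the first mean is 3.1/√150 ≈ 0.25. The plug-in bias in the second row is 4.0 - (-2) = +6.0, a reversal of sign.

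**6. False rejection with a true effect of 0.** Two further simulations of 150 runs per setting, each with 12 adopters of 20 clinics and 100 episodes per clinic-month, used other assumed outcome scales. Their curvature values are not comparable with each other.
- First: with the correct form the plug-in averaged -0.04; with omitted curvature of 0.5 it averaged 7.2 and rejected 26% of the time. Linear 2SLS rejected 0-3%.
- Second: with no omitted curvature the plug-in rejected 6.7% and linear 2SLS 8.7%; with curvature of 0.1 and 0.3 the plug-in rejected 25% and 68%.

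**The case against.** The strongest reply is that the plan already names the right estimator. It specifies 2SLS, makes equation (2) its first stage and plans 2SLS standard errors in Stata. Equation (2) is written linearly in E, and beta_4 is read as an effect on a probability, which suits an identity link. On this reading the mixed model could be a stand-alone referral analysis. This stands as a possible reading, but not the only one: E-hat is defined as a predicted probability from the equation assigned to the mixed model. An identity link would not settle it either, because a mixed fit with a site random effect on top of indicators for the same clinics is not the least-squares first stage.

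A reader might infer that the first stage cannot be fitted as written. The documents do not support that, for three reasons. The link is unstated. The 30-day referral decision window in Section 12.5.2 lets an episode indexed just before activation end in a referral. And Section 12.5.5 also interprets beta_4 as the effect of training; if C meant training, video-phase referrals would fall at C = 0. Either of the last two could make beta_4 finite, though indicators for clinics without referrals would stay separated under a logit or probit link. Even a diverging beta_4 leaves fitted probabilities with a usable limit.

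A reader might also infer that the plug-in is always biased. It showed little or no bias when the covariate form was right. Nor is it true that 2SLS can never carry random effects, since random-effects versions exist; the objection here is duplication of the clinic indicators.

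**Conclusion.** The contradiction is real: the same equation is assigned both a generalized linear mixed model and the first stage of 2SLS, and the identification claim is true only of a linear first stage. How much damage follows depends on the link and on how well the covariate form is specified. With a logit plug-in, 3-5% of the residual variation in E-hat came from C in these simulations, against 100% for linear 2SLS. The bias ranged from slight to a reversal of sign. Those sizes rest on assumed clinic counts, volumes and curvature and are not predictions for this trial.

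A non-finite beta_4 is a further consequence only if the link is logit or probit, C means activation, and no referral falls in a C = 0 episode.

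The point affects Secondary Aim 2 and equation (4), not the primary referral analysis. It should be corrected before analysis because the change is small and the choice should not be left open.

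**What to change.** In Section 12.5.5:

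- Use a linear first stage for equation (2), fitted inside the single planned Stata 2SLS command, with clinic indicators as fixed effects and robust errors clustered by clinic.
- Remove the generalized linear mixed model as the source of E-hat. It may stay as a separate descriptive referral model with its link stated.
- Drop the site random terms that duplicate the clinic indicators.
- Correct the reference from equation (1) to equation (2).
- Define C once, as activation or as training, and use that meaning throughout.
- State that if C is activation and E = 0 whenever C = 0, any complier effect is the effect among referred patients, provided the instrument is valid.

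This costs SAP wording only and needs no new data. It will show less apparent precision than a plug-in (SD 3.1 against 0.7 in the correctly specified simulation), because the plug-in draws its precision from functional form. It does not establish that the instrument is valid: Sections 8.1 and 8.2 invite all clinics in one wave and let them choose, so activation is not randomized, and that needs its own treatment.

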### **6.2.6 Selection of Primary Care Settings**

The primary care setting, as opposed to acute and urgent care centers or specialty clinics, was selected for this study as most patient contacts originate and end in primary care. In many cases, primary care is the only place that individuals have access to care. The primary care setting is the cornerstone of health systems in meeting the broader needs of patients, families, and communities. Primary care practices are tasked with providing high quality care for patients on a long-term basis, many of them with co-morbid conditions that are all positively impacted by greater PA levels. The primary care setting is the first point of contact for patient populations (inactive, with diabetes, hypertension, obesity, and dyslipidemia) requiring primary and/or secondary disease prevention, such as PA promotion and counseling. Further, the primary care setting allows for the ongoing observation of the trajectory of chronic diseases through multiple visits over time. Lastly, the patients seen in primary care settings are representative of the surrounding population, allowing for a greater examination of interventions that reduce health disparities and improve health equity.

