#### **7.4 Determining Patients Eligible for EIMG Referral**

During the data extraction process, a list of patients that were eligible for an EIMG referral (regardless of whether they received a referral or not) will be extracted from the Prisma Health EHR. The research study team will retrospectively identify patients that could have received an EIMG referral based on a list of pre-determined ICD-10 codes.

*Inclusion Criteria.* The study team will develop a list of ICD-10 codes (based off the criteria presented in section 7.2.1.) to identify all potentially eligible patients that could have received an EIMG referral. The ICD-10 codes were selected a-priori by the study team based on the priority health conditions identified by Prisma Health leadership in partnership with the EIMG Advisory Board. These conditions include patients that are physically inactive and/or who have obesity, diabetes, hypertension, or dyslipidemia. The list of ICD-10 codes was selected by the research team and verified by: a) the EIMG Advisory Board, and b) Prisma Health primary care clinicians.

*Exclusion Criteria.* During phase I and II of the study (prior to any extraction of patient data from the Prisma Health EHR), the research team will engage in a process to develop a list of exclusionary criteria. Patients seeking medical assistance with any of these criteria would be deemed ineligible to receive an EIMG referral and will be removed from the denominator of our implementation, reach, and effectiveness analyses. To develop the list of exclusionary criteria, we will engage in a three-step process. First, we will identify published guidelines and existing tools (e.g., PAR-Q+) that list health conditions that are contraindications for physical activity. Second, we will seek the opinions of 8-12 primary care physicians to identify conditions for which they would not refer their patients to a physical activity program. Combining these findings, we will develop a list of ICD-10 codes that will serve as exclusionary criteria for which exercise training is either inappropriate or contraindicated.

*The final list of patients deemed eligible for a referral (inclusion criteria – exclusion criteria) will serve as the ‘denominator’ in our Reach calculations (see 14.1 and 14.2).*

	Definition	Description

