The ratio in equation (4) equals the incremental cost per patient associated with the EIMG referral induced by clinical-level EIMG activation per average change in health outcome associated with the EIMG referral induced by clinical-level EIMG activation. Separate estimates of equation (4) will be calculated by clinical diagnosis using the health outcome change in the denominator most relevant to the specific diagnosis (e.g., change in hemoglobin A1c for type 2 diabetes).

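### The plan asks whether the training effect differs between conditions, but names only separate fits in overlapping strata and gives no test of equal effects

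*Combined protocol and SAP*

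**What the plan says.** Section 12.5.5 sets the question and the method in one sentence: "Secondary analyses will assess differences in the impact of standardized EIMG training by stratifying by eligible conditions", with the conditions listed as "i.e., overweight/obese, hypertension, type 2 diabetes". The model to be stratified is equation (2). Its only training term is the coefficient β4 on C, which "equals the effect of standardized EIMG training on the probability of the patient within the episode being referred to EIMG". There is no product of C with a condition.

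The conditions are not mutually exclusive. Section 7.4 defines eligibility as "physically inactive and/or who have obesity, diabetes, hypertension, or dyslipidemia". Section 6.2.6 describes primary care patients as "many of them with co-morbid conditions that are all positively impacted by greater PA levels". Appendix A lists code Z71.3 under both physical inactivity and obesity. No section says which stratum a patient with several conditions enters.

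The only test of heterogeneity in the plan is the site-by-treatment interaction in Section 12.6. No number of patients per condition is given. The nearest figure is the remark in Section 12.5.5, "Because our expected sample sizes will be greater than 500", which concerns all episodes together.

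**The concern.** The question is comparative, and the named method is not. Three stratified fits give three estimates of β4, and the natural test in each is of no effect in that stratum. None tests whether the three effects are equal. The strata will also differ in size, so the same true effect can be significant in a large stratum and not in a small one.

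Overlap adds a second difficulty. A patient with all three conditions contributes to all three fits. The estimates are then correlated, so they cannot be contrasted as if independent. Each is also a marginal effect, averaged over whatever other conditions the patients in that stratum have. If the effect truly depends on one condition, part of that dependence shows up in the other strata.

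At stake is a statement that training raises referral for one condition and not another when the effect is the same, or a wrong attribution when it is not. Section 5.3 says the economic evaluation, to which this model belongs, may inform coverage and adoption decisions.

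**Working it through.** The documents give no stratum size, overlap or power for this analysis, so there is no planned figure to reproduce. The checks below rest on stated assumptions.

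**1. Disagreement between three equal effects, simplest case.** If each stratum has power p and the strata are independent, the chance that one or two of three are significant is 1 − p³ − (1 − p)³.

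- p = 0.50: 1 − 0.125 − 0.125 = 75%.
- p = 0.78: 1 − 0.4746 − 0.0106 = 51%.
- p = 0.92: 1 − 0.7787 − 0.0005 = 22%.

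The values 0.78 and 0.92 are borrowed from Section 12.3 as reference levels only; they are not stratum powers. Overlap lowers these rates. With correlation 0.5 between the stratum statistics they become 50%, 36% and 17%.

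**2. Simulation with overlap.** Assumptions: prevalences of 60%, 55% and 25%; latent correlation of 0.25 to 0.30, so that about 58% of patients with at least one of the three conditions have two or more; an identical effect in all patients; training contrasted with the video months; tests at 0.05; no clinic terms or clustering.

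Referral in the video months follows Section 12.3: (0.001 + 0.004 + 0.007 + 0.010)/4 = 0.55%. Without a month term, the rate after training is 3.0%, the mean of a linear rise from 0.02 to 0.04 (the accelerated profile). With the month term, the profile is the constant-slope one, 0.031 to 0.040 after training.

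| N | Strata disagree, no month term | Strata disagree, linear month term |
|---|---|---|
| 500 | 45% | 10% |
| 1,000 | 58% | 19% |
| 2,000 | 41% | 27% |
| 5,000 | 6% | 50% |
| 14,000 | 0% | 49% |

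The month term matters because it leaves a smaller and less precise step. In the constant-slope profile the raw before-after difference is 0.0355 − 0.0055 = 0.030, but the step net of trend is 0.031 − (0.010 + 0.003) = 0.018. Power falls, and the N at which disagreement peaks moves up. The accelerated profile with a month term gives lower rates still over this range. A joint test of the three condition-by-training products, without the month term, rejected in 3% to 5% of trials with identical effects.

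**3. A true difference tied to one condition.** Suppose training has no effect in diabetes and +0.0242 in everyone else. A stratum in which a share d also has diabetes shows 0.0242 × (1 − d). The simulated stratum effects were 0.0169 for obesity (0.0169/0.0242 = 0.70, so d is about 30%) and 0.0165 for hypertension (0.0165/0.0242 = 0.68, so d is about 32%). Both appear to respond less well only because they contain patients with diabetes.

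A two-condition version, with additive effects and symmetric overlap, gives the general form: the difference between strata is the true difference × (1 − share of each stratum that also has the other condition). Take a true difference of 0.02.

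- 30% of all patients have both: each stratum holds 0.30 + 0.35 = 0.65, the shared part is 0.30/0.65 = 0.46, and the difference is 0.02 × 0.54 = 0.011.
- 60% have both: each stratum holds 0.80, the shared part is 0.75, and the difference is 0.02 × 0.25 = 0.005.

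The joint model returned 0.020 in both cases.

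**The case against.** Much of the case on the other side stands, and it limits what can be claimed.

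- A reader might infer that the sponsor will compare stratum p-values and call a condition non-responsive. The plan states no such rule. What can be said is that no test of difference is specified and that none follows from stratifying.
- A reader might take a disagreement rate of 40% to 60% as the size of the problem. The table does not support that. The rate moves with N, overlap and the month term. The figure of 500 is a remark about approximate normality, not a planned sample. If the residual SD of 0.01 in Section 12.3 includes binomial noise, the profiles imply at least about 170 to 195 eligible patients per clinic-month; over 10 clinics × 8 months that is 13,600 to 15,600 patient-months.
- A reader might call the stratum estimates biased. They are legitimate marginal effects: the average effect among all patients with hypertension really is lower if some of them also have diabetes that removes it. They mislead only if read as specific to the condition.
- Overlap lowers false disagreement as well as blurring true differences.
- The simulated contrast is video months against training months. Section 12.5.5 defines C by activation, which Section 8.3 places at the video, yet describes β4 as the effect of standardized training. The text is ambiguous, so the simulated contrast is one reading of it.
- A reader might count the sentence "Separate estimates of equation (4) will be calculated by clinical diagnosis" as the same error. It is not: those ratios may use a different health outcome for each diagnosis and state no hypothesis of equality.

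None of this supplies a test of the stated question.

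**Conclusion.** The point holds as a gap in a secondary analysis. Separate fits of equation (2) do not test whether the training effect differs between conditions. Because the strata share patients, the three estimates are correlated and marginal, so a reader of the results could not recover a valid comparison from the separate intervals alone.

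The direction is firm and the size is not. Under the assumptions above, identical effects disagreed on significance in anything from none to somewhat over half of simulated trials. The carry-over of a true difference, about 30% in the diabetes example, depends on the assumed overlap but does not shrink with a larger sample. The change is worth making before the data are analysed. It has no bearing on the primary outcome.

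**What to change.** In Section 12.5.5, replace stratification with one model on all eligible episodes. Keep the clinic and month terms of equation (2), and add an indicator for each of the three conditions and its product with the training variable, on the probability scale that the text uses for β4. Each episode then enters once, with all the patient's conditions. Eligible patients with none of the three, for example with dyslipidemia or inactivity only, form the reference.

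Test the three products jointly. Report each with a confidence interval, using standard errors that allow for clinic clustering and repeated episodes. Show stratum estimates as description only. State whether the training variable means activation or onboard training.

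The cost is a change of SAP wording and three product terms, with no new data. The real drawback is low power: in the two-condition simulation with 6,000 patients, the test of a true difference of 0.02 had 64% power when 30% of patients had both conditions and 41% when 60% did. A non-significant joint test should therefore not be reported as evidence of equal effects. The diagnosis-specific cost-effectiveness ratios are not covered by this change.
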